1. LIST OF ABBREVIATIONS AND ACRONYMS

Term/Abbreviation	Definition
AE	adverse event
AIDS	acquired immune deficiency syndrome
ASPIRE	A Study to Prevent Infection with a Ring for Extended Use
CRF	case report form
CSR	Clinical Study Report
CV	coefficient of variation
DAIDS	Division of Acquired Immunodeficiency Syndrome
DPV	dapivirine
FTC	emtricitabine
GA	gestational age
IQR	interquartile range
IRP	Interim Review Panel
LLOQ	lower limit of quantification
MTN	Microbicide Trials Network
NIAID	National Institute of Allergy and Infectious Diseases
NICHD	National Institute of Child Health and Human Development
NIH	National Institutes of Health
NIMH	National Institute of Mental Health
PO	pregnancy outcome
PPO	post-pregnancy outcome
PrEP	pre-exposure prophylaxis
PROM	premature rupture of membranes
PUEV	product use end/early termination visit
SAE	serious adverse event
SAP	statistical analysis plan
SD	standard deviation
SEV	study exit visit
TFV	tenofovir
TLFs	tables, listings, and figures
VOICE	Vaginal and Oral Interventions to Control the Epidemic

VR	vaginal ring
----	--------------

2. INTRODUCTION

The purpose of this statistical analysis plan (SAP) is to define the analyses that will be conducted to describe mother and infant safety, pregnancy outcomes, pregnancy complications, infant drug levels, adherence, and acceptability for the MTN-042 final protocol analysis.

2.1 General Design Considerations

The following is a summary of Protocol Version 2.0

Short Title:	DELIVER: A Phase 3b Safety Study of the Dapivirine Ring and PrEP in Pregnant Women
IND Sponsor:	DAIDS
Funders:	Division of AIDS, NIAID, NIMH, NICHD, US NIH
Protocol Chair:	[name], MPH [name], MMed
Protocol Co-Chair:	[name], FCPaeds
Sample Size:	Approximately 550 women and their infants
Study Population:	Healthy, HIV-uninfected pregnant females, 18-40 (inclusive) years old, with an uncomplicated singleton pregnancy who are willing to be randomized to study product, and their infants
Study Sites:	MTN-042 site(s) selected by the MTN Executive Committee
Study Hypotheses:	
 • Daily use of Truvada oral tablet and dapivirine (DPV) vaginal matrix ring (25 mg) inserted once every 4 weeks will both be generally safe and well-tolerated by the participants and their fetuses/infants. • Participants who use Truvada oral tablet daily and insert the DPV vaginal matrix ring (25 mg) once every 4 weeks will experience similar distributions of pregnancy outcomes to the general population.
Study Design:	Phase 3b, two-arm, open label, multi-site, randomized (2:1) trial (DPV vaginal ring [VR], Truvada oral tablet), with onset of dosing period to occur within the following gestational age (GA) ranges: 
Cohort 1: 36 0/7 weeks – 37 6/7 weeks 150 women Cohort 2: 30 0/7 weeks – 35 6/7 weeks 150 women Cohort 3: 12 0/7 weeks – 29 6/7 weeks 150 women

Study Duration:	The total duration of study participation for each participant will vary depending on gestational age at time of enrollment and length of pregnancy prior to pregnancy outcome, and will range from approximately 12 weeks or less for Cohort 1 to approximately 36 weeks or less for Cohort 3. Participants who

become infected with HIV will continue in study follow-up with a modified study visit/procedure schedule for a minimum of twelve months. Also, infants born to MTN-042 participants will be followed for approximately 52 weeks (i.e., one year)

Study Products:

- Silicone elastomer matrix VR containing 25 mg of DPV
- Oral tablets (Truvada) containing 200 mg emtricitabine/300 mg tenofovir disoproxil fumarate (FTC/TDF)

Study Regimen:

Within Cohorts 1 and 2, participants will be randomized to the above study products in a 2:1 ratio (VR:tablet). Cohort 3 participants will be randomized to the above study products in a 4:1 ratio (200 VR:50 tablet). Participants randomized to the DPV VR will use one VR continuously for approximately one month, replacing the VR each month. Participants using Truvada tablet will take one tablet orally per day. Participants will use their assigned study product until their pregnancy outcome but no later than 41 6/7 weeks of gestation.

Figure 1: Study Visit Schedule – Cohort 2

Cohort 2	Screening
Enrollment Window	Enrollment
30 0/7 weeks of gestation – 35 6/7 weeks of gestation	1-week (phone, home or clinic as needed per local standard of care)
	2-week
	3-week (phone, home or clinic as needed per local standard of care)
	4-week
	Every odd-numbered week after 36th week of gestation (e.g., follow-up weeks 5, 7, 9) until pregnancy outcome (phone, home or clinic as needed per local standard of care)
	Every even-numbered week including and after 36th week of gestation (e.g., follow-up weeks 6, 8, 10) until pregnancy outcome
Infants enroll →	Post-pregnancy outcome visit (delivery hospital/facility or clinic)
	1-week post-pregnancy outcome (phone, home or clinic as needed per local standard of care)
Mothers exit →	Approximately 6 weeks post-pregnancy outcome
	Approximately 6 months post-delivery
	Approximately 12 months post-delivery

The primary objective of the IRP is to monitor the safety of the products being evaluated and make recommendations about the continuation, modification, or termination of either or both arms of the study in the next gestational age cohort.

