Participants were instructed to use study product until they went into labor. This complicates analyses of laboratory adherence measures (see Section 9.3) taken at the Visit 101 – PPO Visit, since this visit could occur up to 14 days after the pregnancy outcome, i.e., this visit will include time when the participant was expected to not be using study product and drug levels are expected to drop quickly following product discontinuation. This applies to all three laboratory adherence measures, including residual drug levels in VRs since the residual drug measure adjusts for how long the participant had the ring.

Some laboratory adherence measures were tested for a subset of the study population. TFV-DP and FTC-TP were tested for a subset of Cohort 1 mothers (30% of the mothers with a collected sample) (all collected samples were tested for infants, and for mothers in Cohorts 2 and 3). Plasma DPV was tested for a subset of mothers in all three cohorts (50% of the mothers with a collected sample) (all collected samples were tested for infants).

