6.2 Treatment Exposure

As described in Section 3.1 Analysis Set(s), the Product Exposure analysis set will exclude endpoint data that occurs > 7 days after study product discontinuation, and will exclude participants who never received study product.

Study duration, infant study duration, on product duration, on study pregnancy duration, and estimated gestational age at pregnancy outcome will be summarized as continuous variable in tables, by study arm and overall for each of the three cohorts, and for the three cohorts combined.

Study duration will be calculated as the date of study exit (Study Termination CRF) minus the participant's randomization date + 1 day, unless the participant had a termination reason of "Lost to follow-up". If a participant was lost to follow-up then their study duration will be calculated as the date of their last attended visit minus their randomization date + 1 day. The last attended visit is either the last visit with a completed Follow-up Visit Summary CRF, or the last Interim Visit Summary CRF where at least one study procedure was completed (per Interim Visit Summary CRF, "What study procedures were completed at this visit? Select all that apply" item), whichever occurred last.

Infant study duration will be calculated as the date of study exit (Study Termination CRF) minus the infant's birth date + 1 day, unless the infant had a termination reason of "Lost to follow-up". If an infant was lost to follow-up then their study duration will be calculated as the date of their last attended visit minus their birth date + 1 day. The last attended visit is either the last visit with a completed Infant Follow-up Visit Summary CRF, or the last Infant Interim Visit Summary CRF where at least one study procedure was completed (per Interim Visit Summary CRF, "What study procedures were completed at this visit? Select all that apply" item), whichever occurred last.

On product duration will be calculated as the date of product discontinuation (Discontinuation of Study Product CRF) minus the participant's randomization date + 1 day. Only participants who ever received study product will be included in this summary.

On study pregnancy duration will be calculated as the date of the pregnancy outcome (outcome date on Pregnancy Outcome CRF) minus the participant's randomization date + 1 day. Only participants with an obtainable pregnancy outcome will be included in this summary.

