Visit 103 - 6-Week PPO Visit/SEV	42 days after PO	13 days prior to target	13 days after target

*The 1-Week PPO Phone Contact may be skipped if the PPO Visit occurs within the visit window for this phone contact

Table 11: Visit Timing Requirements for Infants

Visit	Target Day	Window Opens	Window Closes
V201 - PPO Visit	as soon after the PO as possible	Pregnancy Outcome	14 days after target
V202 - 1-Week PPO Phone Contact	7 days after PO	6 days prior to target	7 days after target
V203 - 6-Week PPO Visit	42 days after PO	13 days prior to target	13 days after target
V204 - 6-Month PPO Visit	183 days after PO	28 days prior to target	28 days after target
V205 - 12-Month PPO Visit	365 days after PO	28 days prior to target	28 days after target

*The 1-Week PPO Phone Contact may be skipped if the PPO Visit occurs within the visit window for this phone contact

14. APPENDIX III Residual Drug Levels Calculation

The DPV release rate per 28 days of use is calculated as:

$$rate = \frac{(conc_m - conc_r)}{days} \times 28$$

With $conc_m$ being the amount of residual drug in the manufacturer lot, $conc_r$ being the amount of residual drug in the returned ring, and $days$ being the number of days the participant should have been using the ring.

An individual ring is identified in the lab residual DPV data using the `guspec` identifier, with each individual ring having its own unique identifier. Some rings were tested multiple times and will have multiple observations with the same `guspec` value. Observations with censor values of "(A)X", "(A) X", "(B)X", "(B) X", "(B)Z", "(B) Z", or "Z" should not be analyzed. The amount of residual dapivirine in the ring ($conc_r$ above) is indicated by the value of `conc`.

Rings from the lab residual DPV data are linked to the clinical data through the Ring Insertion and Removal CRF, using the participant ID (`ptid`) and specimen collection date (`spcdt`) from the lab data and participant ID and the “Date ring returned” from the CRF data. For participants with multiple rings collected on the same date (i.e., two observations with same `ptid` and `spcdt` and different `guspec`), one ring needs to be assigned to correspond to “ring #1” in the Ring Return section of the CRF, and one to “ring #2”. In this case, the lab observation with the smaller value of `recnum` will be linked to the earlier ring return date on the CRF, and the larger value of `recnum` will be linked to the later ring return date.

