The number of days (*days* in the above equation) is calculated by taking the specimen collection date – “date returned ring #1 was provided” + 1 day (or “date returned ring #2 was provided”), unless the specimen collection date is after the participant’s pregnancy outcome date, in which the duration is calculated as the pregnancy outcome date – “date returned ring #1 was provided” + 1 day.

Ring lot number is determined by linking the “date returned ring #1/#2 was provided” to the Pharmacy Dispensation CRF “date study product dispensed” and taking the “vaginal ring #1 lot number” or “vaginal ring #2 lot number”, as appropriate. That lot number is linked to the manufacturer record of the concentration for that lot ($conc_m$ above).

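### The SAP states the end of product use in two ways, and the Appendix III day count does not stop at a directed end of use, so release rates for some last rings can be biased low

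*SAP*

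**What the plan says.** Three places in the SAP bear on when product use is expected to end.

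- **Section 2.1 (Study Regimen):** "Participants will use their assigned study product until their pregnancy outcome but no later than 41 6/7 weeks of gestation".
- **Section 3.2:** "Participants were instructed to use study product until they went into labor". No gestational-age ceiling is given. The section adds that the post-pregnancy-outcome (PPO) visit complicates the laboratory adherence measures because "this visit could occur up to 14 days after the pregnancy outcome". It extends this to residual drug, "since the residual drug measure adjusts for how long the participant had the ring".
- **Appendix III:** the release rate per 28 days divides the drug lost from the ring by *days*, described as "being the number of days the participant should have been using the ring". In operation, *days* "is calculated by taking the specimen collection date" less the date the ring was provided, plus 1. The exception is collection after the outcome, "in which the duration is calculated as the pregnancy outcome date" less the date provided, plus 1.

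The date on the Discontinuation of Study Product CRF is already in the analysis. It ends on product duration (Section 6.2), sets the 7-day cut-off for the Product Exposure Set (Section 3.1) and, through on product duration, enters the offset of the maternal Poisson model (Section 8.1). Appendix III does not use it.

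Section 9.3 classes the rate as Red (0.9 mg/month or less), Yellow (above 0.9, up to 4.0) or Green (above 4.0).

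**The concern.** The Appendix III denominator is meant to be days of expected use, but the counting rule does not follow that definition. It has no term for onset of labor, for the 41 6/7-week ceiling, or for permanent discontinuation before the outcome. If a woman stops by direction, keeps the unused ring and hands it in later, the days in between count as days on which the ring should have been releasing drug. She then looks less adherent than she was.

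The SAP would also apply two end points to the same woman: the recorded discontinuation date for exposure, and the collection or outcome date for ring adherence. Because Sections 2.1 and 3.2 disagree, a programmer cannot tell from the SAP what the expected end of use is.

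**Working it through.** The SAP gives no figure to reproduce here, so the check applies its own formula.

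**1. Which days the rule removes and which it keeps**

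| Period | Treatment in Appendix III |
|---|---|
| Pregnancy outcome to PPO visit (up to 14 days) | Removed: the count stops at the outcome |
| Onset of labor to outcome, if on different calendar dates | Counted |
| 41 6/7 weeks to outcome, if the ring is returned after the outcome | Counted |
| Directed permanent discontinuation to ring return (or outcome, if earlier) | Counted |
| Any ring exchanged before the end of use | Not affected |

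**2. Effect of surplus days**

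Appendix III: rate = (conc_m − conc_r) / days × 28. Let d be the days of expected use and x the surplus days on which the ring is out of use and releases nothing. The drug lost is the same, so

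reported rate / rate over expected days = d/(d+x), and the relative bias is −x/(d+x).

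The SAP does not give x, so the values below are assumed. The last column is the rate over expected days that a ring must exceed to be reported as Green, 4.0 × (d+x)/d.

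| d | x | Bias | Must exceed (mg/month) |
|---|---|---|---|
| 28 | 1 | −3.4% | 4.14 |
| 28 | 2 | −6.7% | 4.29 |
| 28 | 7 | −20.0% | 5.00 |
| 14 | 1 | −6.7% | 4.29 |
| 14 | 2 | −12.5% | 4.57 |
| 14 | 7 | −33.3% | 6.00 |
| 7 | 1 | −12.5% | 4.57 |
| 7 | 2 | −22.2% | 5.14 |
| 7 | 7 | −50.0% | 8.00 |

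With x = 0 there is no bias. As an example, a 28-day ring at 4.2 mg/month with 2 surplus days is reported as 4.2 × 28/30 = 3.92, which is Yellow instead of Green.

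**3. Where x and short d could come from**

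- *Ceiling:* if use ends at 41 6/7 weeks, the ring is returned after the outcome, and the outcome falls at 42 0/7, 42 3/7 or 43 0/7 weeks, then x is 1, 4 or 8 days.
- *Labor:* x is 1 if labor starts on the calendar day before the outcome.
- *Short last rings:* a woman enrolled at 37 0/7 weeks reaches Week 4 at 41 0/7. If a new ring is supplied then (an assumption, from the monthly replacement in Section 2.1), 41 0/7 to 41 6/7 is 7 days counted inclusively. Appendix I lists no expected visit for this group between Week 4 and the outcome.

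**4. Effect on the tables**

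Section 9.3 assigns rings returned after the last attended bi-weekly visit to Visit 101, so most affected rings should fall in that row and in the row for all visits combined. At participant level, Yellow and Green both count as ever exposed, so a Green-to-Yellow shift changes nothing. Only a shift into Red could matter there. For a 28-day ring with 1 surplus day, that requires a rate over expected days above 0.90 but no higher than 0.9 × 29/28 = 0.93.

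**The case against.** The strongest reply is that the rule mostly works. Appendix III stops at the outcome and so removes the gap of up to 14 days that Section 3.2 names as the problem. If the ring is handed in when use stops, the collection date ends the count correctly. If it stays in place and keeps releasing drug, the extra days do not lower the rate. Labor and outcome often share a calendar date, and the ceiling matters only for pregnancies that pass it. The measure is one descriptive secondary adherence summary with no test. All of this stands, and it limits the size of the problem.

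A reader might infer that ring days routinely include non-use time, so that release rates as a whole are biased low. The documents do not support that. A 28-day ring charged with 14 post-outcome days would lose 1 − 28/42 = 33.3%, but the Appendix III cap prevents this. If Section 2.1 governs, the outcome falls at or before 41 6/7 weeks and product was not permanently discontinued earlier, the bias is zero. A 7-day surplus is an extreme case of unknown frequency.

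It is also fair to object to ending *days* at every discontinuation. That would drop days after a voluntary stop, which an adherence measure may be meant to count. Nor would ring days then equal on product duration, which runs from randomization while ring days run from each ring's provision; only the end point would be shared.

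What the reply does not answer is that the counting rule departs from its own definition for a ring kept out of use after a directed stop, although a usable date is already collected.

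**Conclusion.** The concern holds in a limited form. Sections 2.1 and 3.2 disagree on the end of product use, and the Appendix III count matches its stated definition only when the ring is returned by the end of expected use, or when expected use ends at the outcome.

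The bias is conditional: it needs a last ring, a directed stop (the reconciled end of use, or permanent discontinuation before the outcome), no drug release afterwards, and return after the stop. Under those conditions the rate is low by x/(d+x). For 1 or 2 surplus days this is a few percent on a full-length ring and 12.5% to 22% on a 7-day ring. The consequence is possible Green-to-Yellow misclassification at visit level, with the participant-level result largely protected. The number of affected rings and the distribution of x cannot be derived from the SAP. The correction is worth making because it is specific and cheap; the primary endpoints are not touched.

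**What to change.** 1. Reconcile Sections 2.1, 3.2 and Appendix III on the end of expected product use. This review does not say which rule should stand.
2. In Appendix III, end *days* at the earliest of specimen collection, pregnancy outcome, and the Discontinuation of Study Product CRF date where product use ended by direction. The SAP cites no field for onset of labor, so if that rule is kept, say which recorded date represents it.
3. State separately how days after a participant's voluntary stop are counted, for example with a sensitivity summary with and without them. The primary-reason item tabulated in Section 6.4 may allow the two kinds of stop to be told apart; its response options are not shown in the SAP, so this needs checking.
4. Align the Section 3.2 remark on residual drug at the PPO visit with the outcome-date cap in Appendix III.

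The cost is SAP wording, one extra merge with a CRF already in use and, if chosen, one additional summary.

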2.2 Study Objectives and Endpoints

Primary Objectives:

Maternal and Infant Safety: To describe the maternal and infant safety profile associated with

study product exposure during pregnancy

Pregnancy Outcomes: To describe the pregnancy outcomes associated with study product exposure during pregnancy

Primary Endpoints:

-

Maternal Safety (composite)

- All serious adverse events, including maternal deaths
- All Grade 3 or higher adverse events (AE) as defined by the Division of AIDS (DAIDS) Table for Grading the Severity of Adult and Pediatric Adverse Events, Corrected Version 2.1, July 2017 and/or Addendum 1 (Female Genital Grading Table for Use in Microbicide Studies [Dated November 2007])

Infant Safety (composite)

- All serious adverse events, including infant deaths and congenital anomalies
- All Grade 3 or higher AEs as defined by the Division of AIDS (DAIDS) Table for Grading the Severity of Adult and Pediatric Adverse Events, Corrected Version 2.1, July 2017

Pregnancy Outcomes

- Frequency of the following pregnancy outcomes:
 - Full term live birth (≥ 37 0/7 weeks)
 - Premature live birth (< 37 0/7 weeks)
 - Pregnancy loss (≥ 20 0/7 weeks)
 - Pregnancy loss (< 20 0/7 weeks)

Secondary Objectives:

Pregnancy Complications: To describe pregnancy complications associated with study product exposure during pregnancy

Infant Drug Levels: To describe infant levels of study drugs associated with study product exposure during pregnancy

Adherence: To characterize adherence to open label use of the DPV VR (25 mg) and oral Truvada in pregnant women

Acceptability: To characterize acceptability of open label use of the DPV VR (25 mg) and oral Truvada in pregnant women

Secondary Endpoints:

Pregnancy Complications

- Frequency of the following pregnancy complications:
 - Hypertensive disorders of pregnancy
 - Chorioamnionitis
 - Puerperal sepsis and endometritis
 - Antepartum, intrapartum and postpartum hemorrhage
 - Preterm premature rupture of membranes (PROM)
 - Fever of unclear etiology

Infant Drug Levels

- Infant blood tenofovir diphosphate (TFV-DP) and emtricitabine triphosphate (FTCTP) concentrations
- Infant plasma DPV concentrations

Adherence

- Maternal blood TFV-DP and FTC-TP concentrations
- Maternal plasma DPV concentrations
- Participant report of frequency of study product use (e.g., missed doses for oral Truvada and VR removal/expulsions [voluntary and involuntary] and duration without VR in vagina)
- Residual drug levels in returned VRs

Acceptability

- Self-reported attitudes about study product attributes and willingness to use study products during pregnancy
- Proportion of participants who find the study products to be at least as acceptable as other HIV prevention methods

2.3 Randomization

Participants in Cohorts 1 and 2 were randomized in a 2:1 ratio to the two arms of the study, two DPV VR to one FTC/TDF, stratified by study site. Participants in Cohort 3 were randomized in a 4:1 ratio, four DPV VR to one FTC/TDF, also stratified by study site.

2.4 Blinding

This was an open label study. Study staff and participants were blinded to the sequence prior to randomization of the participant.

2.5 Primary Study Hypotheses

- It is hypothesized that daily use of Truvada oral tablet or DPV vaginal matrix ring (25 mg) inserted once every 4 weeks will be generally safe and well-tolerated by the participants and their fetuses/infants.
- It is hypothesized that participants who use Truvada oral tablet daily or insert the DPV vaginal matrix ring (25 mg) once every 4 weeks will experience similar distributions of pregnancy outcomes to the general population.

